1.1 Razuprotafib and the Tie2 Pathway

Tie2 is the receptor for the angiopoietin (Angpt) family of secreted proteins and is expressed on vascular endothelial cells throughout the adult vasculature, including pulmonary endothelial cells. Tie2 activation is required for maintaining normal endothelial function and the overall stability of the quiescent, adult vasculature.^{8,9} Over the past decade, endothelial dysfunction and vascular destabilization due to reduced Tie2 activation have been implicated in the pathophysiology of a variety of acute and chronic conditions characterized by endothelial dysfunction, vascular injury, DIC, and inflammation, including acute respiratory distress syndrome (ARDS) and now COVID-19.^{8,10,11,12,13} Providing a clinical correlate and biomarker of reduced Tie2 activation, multiple studies have shown that circulating Angpt-2, a Tie2 conditional antagonist ligand, is increased in patients with either sepsis and/or ARDS and correlates with clinical severity and mortality.^{14,15,16,17,18} Thus, restoring Tie2 activation could be an effective host-targeted intervention to ameliorate progression of pulmonary and vascular pathology in COVID-19.

Vascular endothelial protein tyrosine phosphatase (VE-PTP), the molecular target for razuprotafib, is a receptor tyrosine phosphatase expressed on vascular endothelial cells that blocks Tie2 signaling by dephosphorylating phosphotyrosine residues on Tie2 required for signal transduction.^{19,20}

Razuprotafib is a novel small molecule that restores Tie2 activation by inhibiting the catalytic domain of VE-PTP. Notably, inhibition of VE-PTP with razuprotafib increased Tie2 phosphorylation in cultured endothelial cells even in the absence of Angpt-1 or Angpt-2 and enhanced the agonist properties of both ligands.¹⁹

Importantly, preclinical data show that razuprotafib, via Tie2 pathway activation, has pleiotropic actions to improve endothelial function and stabilize the vasculature. For example, razuprotafib stabilized endothelial junctions, via Tie2-mediated activation of Rap1, leading to dissolution of radial stress fibers via Rac1 and suppression of nonmuscle myosin II.²¹ In addition, treatment of

endothelial cells with razuprotafib dose-dependently increased the phosphorylation of endothelial nitric oxide synthase (eNOS) on serine 1177, a marker of eNOS activation.¹⁹ Nitric oxide (NO), generated by activation of eNOS, is a crucial mediator of normal endothelial vasodilatory, anti-thrombotic, and anti-inflammatory functions.^{22,23} In addition, local generation of NO could have direct inhibitory effects on coronavirus replication.²⁴ Furthermore, disruption of the endothelial Tie2 axis has also been demonstrated to be a critical event in septic DIC,¹² making razuprotafib a strong candidate for addressing such conditions now shown to be associated with poor COVID-19 outcomes.

In vivo, subcutaneous (SC) administration of razuprotafib restores Tie2 activation and reduces lipopolysaccharide (LPS)/endotoxin-mediated vascular leakage and leukocyte transmigration (neutrophil and lymphocyte) in the lung, two key components of COVID-19 and ARDS pulmonary pathology that contribute to respiratory failure.²¹ Razuprotafib also reduced lung toxicity and improved survival in mouse models of interleukin (IL)-2-induced cytokine storm, possibly relevant to the cytokine storm that is associated with poor outcomes in COVID-19.^{25,26,27} Consistent with potential benefits in other vascular beds commonly affected in COVID-19, razuprotafib restored Tie2 activation and improved outcomes in an LPS-induced acute renal injury model (AKB-9778-NC-0084). In addition, VE-PTP inhibition with AKB-9785, a close chemical congener of razuprotafib, showed improved outcomes in a transient middle cerebral artery occlusion stroke model.²⁸

Importantly, in conditions associated with chronic endothelial dysfunction and vascular injury such as diabetes and hypertension, VE-PTP expression is increased and Tie2 activation is decreased, possibly explaining the predisposition of patients with these conditions for increased severity of COVID-19.^{29,30,31,32} Moreover, VE-PTP is highly expressed in the lung, and VE-PTP expression is increased and Tie2 activation is decreased by hypoxia, perhaps contributing to the rapid deterioration and multiorgan failure that occurs in COVID-19 patients with severe respiratory failure.^{19,29}

1.2 Clinical Development of Razuprotafib

The efficacy of razuprotafib in humans has not been tested in clinical studies for the treatment of COVID-19. However, SC administration of razuprotafib has been assessed in patients with clinically significant diabetic eye disease. In early human SC injection studies, razuprotafib absorption was demonstrated to be very rapid, with maximum plasma concentration (C_{max}) achieved within 15 to 30 minutes after dosing, followed by a rapid decline in concentrations with an elimination half-life ($T_{1/2}$) of approximately 1 hour across a wide dose range (5 to 80 mg single doses [AKB-9778-CI-2001]). The short $T_{1/2}$ supported no significant accumulation when multiple doses were administered using a twice daily (BID) regimen for a dose range of 5 to 30 mg BID (AKB-9778-CI-2002). As an indicator of target engagement consistent with eNOS activation downstream of Tie2, there was a dose-dependent reduction in blood pressure in a 1-month Phase 1b study, TIME1 (AKB-9778-CI-2002), which corresponded with the plasma concentration profile. In a 3-month Phase 2 study, TIME2 (AKB-9778-CI-2003), the bulk of the reduction in blood pressure occurred in patients with baseline systolic blood pressures >140 mmHg versus very little reduction in patients with baseline systolic blood pressures <140 mmHg, consistent with enhanced endothelial function in the hypertensive, diabetic patients.

Other end-organ readouts of vascular stability in the context of diabetes are also improved by razuprotafib. In a Phase 2 study in patients with diabetic macular edema (AKB-9778-CI-2003),

SC razuprotafib 15 mg BID combined with monthly intravitreal injections of the anti-vascular endothelial growth factor (VEGF) compound ranibizumab (Lucentis[®]) resulted in a highly statistically significant reduction in retinal thickness compared to either agent alone. This was the first demonstration of a clinical benefit in a randomized, placebo-controlled study of any therapy in combination with anti-VEGF in diabetic macular edema.³³ Furthermore, among patients with evidence of diabetic nephropathy (urine albumin/creatinine ratio [UACR] ≥ 30 mg/g), razuprotafib reduced UACR by approximately 20% compared to an increase in UACR among patients treated with Lucentis alone, indicative of a potential beneficial effect on renal function.

In a Phase 2 study, TIME2b (AKB-9778-CI-5001), in patients with non-proliferative diabetic retinopathy, SC razuprotafib 15 mg BID for 48 weeks in patients with significant albuminuria (UACR >30 mg/g) again reduced UACR by approximately 20% compared to an increase in patients receiving placebo. Thus, the evidence of target engagement indicated by the blood pressure effect and evidence of efficacy suggested by the beneficial effects in the diabetic retina and kidney, together with data from multiple preclinical models, support further evaluation of razuprotafib in patients with COVID-19.

1.3 Study Rationale

Razuprotafib represents a unique, first-in-class, host-targeted intervention to ameliorate progression of pulmonary and vascular pathology in COVID-19, potentially meeting an urgent unmet medical need. A Phase 2 clinical study (RESCUE) has been designed to test the safety and efficacy of SC administration of razuprotafib to reduce the severity of pulmonary and vascular pathology in patients with moderate to severe COVID-19. This would likely result in earlier recovery, fewer patients requiring mechanical ventilation, decreased time in the ICU on ventilator support, and concomitant reduction in morbidity and mortality. Additionally, razuprotafib together with emerging antiviral drugs and other therapeutics could provide the optimal combination of host and virus targeted therapy for the treatment of COVID-19.

1.4 Risk/Benefit

In the completed clinical studies AKB-9778-CI-2003 and AKB-9778-CI-5001, the frequency and other characteristics of serious adverse events (SAEs) and events leading to discontinuations were generally consistent with those anticipated in the primarily diabetic population evaluated in these studies and were generally similar between the razuprotafib and control groups. All SAEs to date have been reported as unrelated, and no serious adverse reactions have been reported. Based on all available safety information from nonclinical and clinical studies, the overall benefit-risk profile of razuprotafib appears favorable. Given the potential beneficial effect of razuprotafib in patients with endothelial dysfunction and vascular injury, evaluation of razuprotafib in clinical studies for the treatment of moderate to severe COVID-19 is considered justified.

1.5 Intent to Benefit

All study participants will receive additional safety monitoring as required per the research protocol which they are participating, in addition to the standard of care they would receive and would still receive, if they did not participate in the trial. While standard of care varies by institution, the additional safety monitoring all study participants will receive per the AKB-9778-CI-6001 protocol includes but is not limited to: increased vital signs monitoring (blood pressure,

heart rate, oxygen saturation); additional blood chemistry, hematology, and coagulation testing; electrocardiograms; additional oversight from local study physician(s), nurses, and research staff as well as physicians and medical personnel at the Sponsor and the CRO; and continued follow up and monitoring after hospital discharge.

Standard of care varies per institution and even more so under resource limitations brought on by COVID-19. Due to this, participation in this clinical trial provides every subject with a more personalized and thorough hospital experience provided for by the designated study clinical team in addition to the standard of care team, with continued oversight following discharge through Day 28. Patients or LARs who do not participate in this trial are likely not able to easily connect with the same physician(s) who managed their care while hospitalized or connect with a physician at all. It may also be that these patients are unsure of when/how to reach out to their treating physician. With a clear mechanism of follow up defined in the study protocol, these patients or LARs can discuss post-hospitalization status with their study physician allowing early identification of any lingering COVID-19-related sequelae. This post-hospitalization follow up, and even continued follow up if still hospitalized, will lead to better outcomes for all participants.

.

2 STUDY OBJECTIVES

2.1 Primary Objectives

The primary objectives of this study are to assess the safety and efficacy of razuprotafib in subjects with moderate to severe COVID-19.

2.2 Secondary Objectives

The secondary objectives of this study are to examine the effects of razuprotafib on biomarkers of inflammation and coagulopathy (ie, C-reactive protein [CRP] and D-dimer) in the plasma of subjects with moderate to severe COVID-19 and to characterize exposure of razuprotafib based on plasma concentrations for the samples collected on Day 1 and Day 6.

2.3 Exploratory Objective

[figure not shown]
The exploratory objective of this study is to examine the effects of razuprotafib on biomarkers of vascular leakage and inflammation (ie, Angpt-2, IL-6, IL-8, tumor necrosis factor alpha [TNF α], and high mobility group box 1 [HMGB-1]) in the plasma of subjects with moderate to severe COVID-19.

3 STUDY DESCRIPTION

3.1 Summary of Study Design

This is a Phase 2, randomized, double-blind, placebo-controlled, parallel-group, multicenter, dose escalation and proof-of-concept study to evaluate the safety and efficacy of razuprotafib, administered three times daily (TID) (every 8 hours [Q8H]), in hospitalized subjects with moderate to severe COVID-19 receiving standard of care therapy. The study design is summarized in Figure 1.

Figure 1. Study Design Schematic

Abbreviations: AE = adverse event; DRC = Data Review Committee; POC = proof-of-concept; TID = three times daily.

The study is planned to include 2 parts as described below.

Part 1

Part 1 will be a 2-step dose escalation that includes approximately 60 subjects. Part 1, Step 1 will include approximately 30 subjects, and Part 1, Step 2 will include approximately 30 subjects. Part 1 will primarily focus on safety; however, efficacy data will be collected and analyzed as well.

Part 1, Step 1: For subjects enrolled in Part 1, Step 1, 6 sentinel subjects will be randomized to receive either razuprotafib 10 mg TID, razuprotafib 20 mg TID, or placebo TID (ie, 2 subjects will receive razuprotafib 10 mg TID, 2 subjects will receive razuprotafib 20 mg TID, and 2 subjects will receive placebo TID). The DRC will convene to recommend if continuation of Part 1, Step 1 as planned is acceptable or if dosing modifications are required once adverse event (AE) information through at least 8 hours following the first dose of study drug is available for all 6 sentinel subjects.

If it is decided that Part 1, Step 1 should proceed as planned, then approximately 24 subjects will be randomized to 1 of 3 treatment groups (razuprotafib 10 mg TID, razuprotafib 20 mg TID, or placebo TID) in a 1:1:1 ratio according to a computer-generated randomization list and stratified by disease severity. Subjects with moderate COVID-19 will comprise a maximum of

approximately 50% of the subjects enrolled in Part 1, Step 1. After the last subject enrolled in Part 1, Step 1 completes the Treatment Period, the Data Review Committee (DRC) will convene to review available safety and pharmacokinetic (PK) data as defined in the DRC Charter.

Part 1, Step 2: The DRC will recommend if dose escalation to razuprotafib 30 mg TID is acceptable as planned, or if enrollment should continue with 1 or more lower doses. If the DRC recommends that Part 1, Step 2 should proceed as planned, then 6 sentinel subjects will be randomized to receive either razuprotafib 20 mg TID, razuprotafib 30 mg TID, or placebo TID (ie, 2 subjects will receive razuprotafib 20 mg TID, 2 subjects will receive razuprotafib 30 mg TID, and 2 subjects will receive placebo TID). The DRC will convene to recommend if continuation of Part 1, Step 2 as planned is acceptable or if dosing modifications are required once AE information through at least 8 hours following the first dose of study drug is available for all 6 sentinel subjects.

If it is decided that Part 1, Step 2 should proceed as planned, then approximately 24 subjects will be randomized to 1 of 3 treatment groups (razuprotafib 20 mg TID, razuprotafib 30 mg TID, or placebo TID) in a 1:1:1 ratio according to a computer-generated randomization list and stratified by disease severity. If it is decided that only 1 dose level will be evaluated in Part 1, Step 2, then subjects will be randomized to 1 of 2 treatment groups (razuprotafib or placebo) in a 2:1 ratio (razuprotafib:placebo). The placebo volume will match the active volume for each treatment group. Subjects with moderate COVID-19 will comprise a maximum of approximately 50% of the subjects enrolled in Part 1, Step 2. After the last subject enrolled in Part 1, Step 2 completes the Treatment Period, the DRC will convene to review all available safety and PK data from Part 1, Step 1 and Part 1, Step 2 as defined in the DRC Charter.

Part 2

Part 2 will be a proof-of-concept safety and efficacy study that will include approximately 120 subjects. Based on the DRC's review of the available safety and PK data from Part 1, Step 1 and Part 1, Step 2, the study will proceed to Part 2, and the DRC will recommend either 1 or 2 doses of razuprotafib to evaluate up to 30 mg TID. Subjects will be randomized to 1 of the treatment groups (dose 1 razuprotafib TID, dose 2 razuprotafib TID [optional], or placebo TID) in a 1:1:1 ratio (or a 2:1 ratio [razuprotafib:placebo] if only 2 treatment groups) according to a computer-generated randomization list and stratified by disease severity. The placebo volume will match the active volume for each treatment group. Subjects with moderate COVID-19 will comprise a maximum of approximately 50% of the subjects enrolled in Part 2. The DRC will convene at increments of approximately 25% enrollment in Part 2 to review all available safety and PK data as defined in the DRC Charter.

3.1.1 Overview of Study Schedule for All Subjects

After consent for study participation is obtained and eligibility is determined, subjects will be randomized to 1 of the treatment groups as described above. Treatment group assignment will be blinded to subjects, clinicians, Sponsor study team, Contract Research Organization (CRO) study team, and Investigators. Subjects will be dosed SC in the abdomen TID for 7 days or until discharge from the hospital (or death), whichever occurs first. Prior to the initiation of Part 2, the DRC may make a recommendation to increase the study drug dosing duration to up to 14 days. Subjects will be followed for safety and efficacy through Day 28 at on-site visits if the subject has not been discharged or via telephone visits if the subject has been discharged. If a subject reports

a decline in clinical status at a telephone visit, then per the discretion of the Investigator, the subject will be requested to return to the site for an Unscheduled Visit. See [Appendix A](#) for a list of assessments to be performed at the Unscheduled Visit.

In addition to the routine clinical monitoring that is part of standard of care, the following will be conducted: vital signs, blood chemistry, hematology, and coagulation will be assessed during the Treatment Period and until Day 28, unless discharged; 12-lead electrocardiograms will be performed at Screening, on Day 7 (or at discharge if subject is discharged prior to Day 7), and on the last day of dosing if the study drug dosing duration is increased to up to 14 days; data on the subject's oxygen support requirements (ie, peripheral capillary oxygen saturation [SpO_2]:fractional inspired oxygen [FiO_2] ratio or partial pressure of oxygen [PaO_2]: FiO_2 ratio if arterial blood gas is being performed per standard of care) will be collected during the Treatment Period and until Day 28, unless discharged; clinical status based on the National Institute of Allergy and Infectious Diseases (NIAID) 8-point ordinal scale and AEs will be assessed through Day 28; blood sampling for PK analysis will occur on Day 1 and Day 6 for Part 1 and may occur for Part 2; and blood sampling for biomarkers associated with coagulation, inflammation, and vascular leakage (CRP and D-dimer assessed at local laboratory; Angpt-2, IL-6, IL-8, TNF α , and HMGB-1 assessed at central laboratory) will occur at Screening and on Day 7 (or at discharge if subject is discharged prior to Day 7) for all subjects. If the study drug dosing duration is increased to up to 14 days, blood sampling for biomarkers will also occur on the last day of dosing. For all subjects remaining hospitalized on Day 14 or beyond, blood sampling for biomarkers will also occur on Day 28 or the day of hospital discharge, whichever occurs first.

The duration of the study for each subject will be approximately 29 days: Screening (approximately 1 day), Treatment Period (7 days [or up to 14 days if recommended by the DRC]), and Post-Treatment Observation Period (approximately 21 days [or 14 to 20 days if Treatment Period is extended]).

The study will take place at approximately 20 sites in the United States.

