5.2 Rationale for Dosing

Previous clinical studies with razuprotafib have evaluated 15 mg and 30 mg BID dosing regimens, administered by SC injection, in diabetic patients with eye diseases. In all of the studies conducted, razuprotafib has exhibited a predictable, dose-dependent PK profile. Also, the results have clearly confirmed target engagement of razuprotafib as evidenced by a dose-dependent decrease in blood pressure, the effect that has been associated with a downstream effect of razuprotafib on Tie2 activation resulting in an increase in eNOS. The effect on blood pressure has been transient in duration and is a function of the C_{max} value for the razuprotafib dose. In human studies, the PK profile exhibited a rapid increase in plasma concentration after SC dose administration with time to C_{max} values achieved within 15 to 30 minutes, followed by a rapid decline with a $T_{1/2}$ of approximately 1 hour. Due to the short $T_{1/2}$, no significant razuprotafib accumulation is expected when administered on a TID regimen in this study.

Based on the unknown pharmacologic effects of razuprotafib in patients with COVID-19, this study is designed as a 2-part, placebo-controlled, parallel-group study with appropriate safety monitoring and PK assessments (see [Figure 1](#)). Part 1 will be a 2-step dose escalation conducted in approximately 60 subjects assessing doses of up to 30 mg TID, and Part 2 will be a

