8.9 Vital Signs

Vital signs will be collected as indicated in [Appendix A](#). Vital signs will include blood pressure, heart rate, SpO₂ (for non-ventilated subjects only), and respiratory rate. If vital signs are to be assessed at the same time point as a blood draw, vital signs should be assessed prior to blood draw. Vital signs will be assessed within 1 hour prior to each dose of study drug and 30 (± 15) minutes, 60 (± 15) minutes, and 90 (± 15) minutes following each dose of study drug. Additionally, after the first dose of study drug, supine blood pressure will be assessed every 5 (± 1) minutes for the first 15 minutes, and then every 15 (± 5) minutes for the first hour. Subjects will be in the supine position during dosing, and they must remain supine with their head no higher than 45° until the vital sign assessment is completed 90 minutes following dosing. After the Treatment Period, vital signs will be assessed daily until Day 28, unless discharged.

Temperature will be measured at Screening only.

8.10 12-lead Electrocardiogram

12-lead electrocardiograms will be performed as indicated in [Appendix A](#). If a 12-lead electrocardiogram was performed within 24 hours prior to informed consent, it is not necessary to repeat the 12-lead electrocardiogram at Screening.

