APPENDIX A: SCHEDULE OF PROCEDURES

Day (± Visit Window)	Screening ^a See Footnote ^a	Treatment Period							Post-Treatment Observation Period ^b			Unscheduled Visit ^b
		1	2	3	4	5	6	7 ^c	14 (±2 d)	21 (±2 d)	28 (±3 d)	
Informed consent ^d	X											
Eligibility criteria	X											
Demographic information	X											
Medical history	X											
Prior/concomitant medications	X	X	X	X	X	X	X	X	X	X	X	X
Urine pregnancy test ^{e,f}	X											
Blood chemistry, hematology, and coagulation ^{f,g}	X	X		X		X		X	X	X	X	X
SARS-CoV-2 test ^{f,h}	X											
Blood sampling for PK ⁱ		X					X					
12-lead electrocardiogram ^j	X							X				
Temperature	X											
Vital signs ^k	X	X	X	X	X	X	X	X	X	X	X	X
Pulse oximeter for SpO ₂ :FiO ₂ or ABG ^{f,l} for PaO ₂ :FiO ₂ ^m	X	X	X	X	X	X	X	X	X	X	X	X
Clinical status ⁿ	X	X	X	X	X	X	X	X	X	X	X	X
Blood sampling for CRP and D-dimer biomarkers ^{f,o}	X							X				X
Blood sampling for vascular leakage and inflammation biomarker ^{s,p,o}	X							X				X
Randomization ^q		X										
Study drug administration ^r		X	X	X	X	X	X	X				
Adverse events		X	X	X	X	X	X	X	X	X	X	X

Note: This Schedule of Procedures does not include assessments that are part of standard of care.

- Unless otherwise specified, all Screening assessments must be performed within 24 hours prior to randomization. The Screening and Day 1 procedures may be performed on the same calendar day. Study Days may not correspond exactly with calendar days.
- During the Post-Treatment Observation Period, the site will perform weekly telephone visits for subjects who have been discharged to assess concomitant medications, clinical status, and adverse events. If a subject reports a decline in clinical status at a telephone visit, then per the discretion of the Investigator, the subject will be requested to return to the site for an Unscheduled Visit. For subjects who remain in the hospital during the Post-Treatment Observation Period, assessments will be performed at the site as indicated.
- For subjects who are discharged prior to Day 7, all of the Day 7 procedures will be performed on the day of discharge. For subjects who are discharged on Days 1 through 4, concomitant medications, clinical status, and adverse events will be assessed by a telephone visit on Day 7 (±2 d). If a subject discontinues from study drug prematurely, site

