- j. If a 12-lead electrocardiogram was performed within 24 hours prior to informed consent, it is not necessary to repeat the 12-lead electrocardiogram at Screening.
- k. Vital signs will include blood pressure, heart rate, SpO₂ (for non-ventilated subjects only), and respiratory rate. If vital signs are to be assessed at the same time point as a blood draw, vital signs should be assessed prior to blood draw. Vital signs will be assessed within 1 hour prior to each dose of study drug and 30 (\pm 15) minutes, 60 (\pm 15) minutes, and 90 (\pm 15) minutes following each dose of study drug. Additionally, after the first dose of study drug, supine blood pressure will be assessed every 5 (\pm 1) minutes for the first 15 minutes, and then every 15 (\pm 5) minutes for the first hour. Subjects will be in the supine position during dosing, and they must remain supine with their head no higher than 45° until the vital sign assessment is completed 90 minutes following dosing. After the Treatment Period, vital signs will be assessed daily until Day 28, unless discharged.
- l. ABG should be obtained only if clinically indicated. If ABG is obtained, the subject's current oxygen requirement should also be recorded.
- m. During the Treatment Period, SpO₂:FiO₂ or PaO₂:FiO₂ (if ABG is being performed per standard of care) will be assessed TID, within 1 hour prior to each dose of study drug. After the Treatment Period, SpO₂:FiO₂ or PaO₂:FiO₂ (if ABG is being performed per standard of care) will be assessed daily until Day 28, unless discharged.
- n. During the Treatment Period, clinical status will be assessed TID, within 1 hour prior to each dose of study drug, using the NIAID 8-point ordinal scale. After the Treatment Period, clinical status will be assessed once daily until Day 28, unless discharged. If the subject is discharged alive prior to Day 28, clinical status will be assessed at the Post-Treatment Observation Period telephone visits only.
- o. For all subjects remaining hospitalized on Day 14 or beyond, blood sampling for biomarkers will also occur on Day 28 or the day of hospital discharge, whichever occurs first.
- p. Vascular leakage and inflammation biomarker (Angpt-2, IL-6, IL-8, TNF α , and HMGB-1) analysis will be performed at a central laboratory.
- q. After it is determined that all eligibility criteria have been met, the subject will be randomized.

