3.6.1 Adverse Events (AEs)

AEs, which include clinical laboratory test variables, will be monitored and documented from the time of the first dose of study drug until Day 28. All AEs will be coded to system organ class and preferred term using MedDRA version 23.0. Treatment-emergent adverse events (TEAEs) will be defined as an event that occurs on or after the first dose of study drug.

An overview of AEs will be provided including counts and percentages of subjects and event counts with the following:

- Any TEAEs (Overall, by maximum severity)
- Any study drug related TEAEs
- Any treatment-emergent serious AEs (TESAEs)

- Any TEAEs leading to discontinuation of study drug
- Any TEAEs leading to death

Counts and percentages of subjects and event counts will also be presented by system organ class and preferred term for each of the categories in the overview.

All AEs will be displayed in listings. In addition, listings will be presented specifically for SAEs and TEAEs leading to discontinuation of study drug.

3.6.2 *Clinical Laboratory Tests*

Values and changes from baseline of clinical laboratory variables for blood chemistry, hematology, and coagulation will be summarized using descriptive statistics by treatment group and time point. The number of available observations and out-of-range values (absolute and in percentage) will also be presented by treatment group. Clinical Laboratory data will be listed.

3.6.3 *Vital Signs*

Vital signs will include blood pressure, heart rate, SpO2 (for non-ventilated subjects only), and respiratory rate. Temperature will be measured at Screening only.

Values, changes from baseline, changes from pre-dose for each TID dose of vital signs will be summarized using descriptive statistics by treatment group and time point. Vital signs will be listed.

3.6.4 *Electrocardiograms*

Values and changes from baseline of electrocardiograms data will be summarized using descriptive statistics by treatment group and time point (baseline and Day 7). The overall interpretation will be summarized by counts and percentages by treatment group and total. 12-lead electrocardiograms data will be listed.

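### The on-treatment 12-lead ECG is not timed to a dose, so it will probably miss peak exposure and has low sensitivity to a Cmax-related effect

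*Protocol*

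**What the plan says.** Protocol 3.1.1 (repeated in the synopsis) sets the schedule: "12-lead electrocardiograms will be performed at Screening, on Day 7 (or at discharge if subject is discharged prior to Day 7"). The same sentence then provides for one more tracing, which depends on a longer treatment course: "and on the last day of dosing if the study drug dosing duration is increased to up to 14 days". With 7-day dosing there is therefore one scheduled tracing after baseline.

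Protocol 8.10 adds no timing of its own and refers the reader to Appendix A. In Appendix A the ECG row is marked at Screening and Day 7, and its one footnote concerns Screening only: "If a 12-lead electrocardiogram was performed within 24 hours prior to informed consent, it is not necessary to repeat the 12-lead electrocardiogram at Screening". For early discharge, "For subjects who are discharged prior to Day 7, all of the Day 7 procedures will be performed on the day of discharge", again with no reference to the last dose. Section 4.5 asks subjects who stop study drug early to complete the Day 7 panel without the dose, so some Day 7 tracings may be off drug.

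SAP 3.6.4 reads: "Values and changes from baseline of electrocardiograms data will be summarized using descriptive statistics by treatment group and time point (baseline and Day 7"). SAP 3.1.3 uses nominal visits with no analysis windows. The last-dosing-day ECG is not listed as a time point.

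Other measurements are tied to the dose. Vital signs are taken before each dose and at 30, 60 and 90 (±15) minutes after it (8.9). PK samples are taken at 30 and 90 (±15) minutes after the first dose of the day on Days 1 and 6 (7.4). SAP 3.6.3 analyses vital signs as change from pre-dose for each dose.

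**The concern.** ECG is one of four components by which the protocol says safety will be judged (8.7; also SAP 3.6). Section 5.2 describes a drug that peaks and clears quickly: time to Cmax "values achieved within 15 to 30 minutes, followed by a rapid decline with a" half-life of about 1 hour. It also describes the known blood-pressure effect as transient and a function of Cmax. The vital-sign schedule follows that reasoning, but the ECG schedule does not.

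If an ECG effect also tracked concentration, a tracing at an arbitrary point in an 8-hour interval would usually be taken well after the peak. The Day 7 summary would then mix tracings near peak, far from peak and off drug. Nothing in the planned output would let a reader separate them. A flat comparison with placebo would be weak evidence against a peak-related effect.

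**Working it through.** The documents give no exposure or precision figure for the ECG, so there is nothing to reproduce. The check asks where in the concentration curve an untimed tracing would fall.

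**Inputs**
- Time to Cmax 0.25 to 0.5 h; half-life about 1 h (Protocol 1.2 and 5.2).
- Dosing interval τ = 8 h (Protocol 5.5.3).
- ECG time uniform over the interval. This is an assumption; the documents give no distribution.
- Half-life varied from 0.75 to 1.5 h, as an assumed range around the approximate 1 h.

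**Simple decline.** If the concentration halves every hour after Tmax, the share of the interval below a fraction p of Cmax is [8 − (Tmax + log2(1/p))]/8.
- p = 0.5: (8 − 1.25)/8 = 84.4% and (8 − 1.5)/8 = 81.2%.
- p = 0.1, with log2(10) = 3.32: (8 − 3.57)/8 = 55.4% and (8 − 3.82)/8 = 52.2%.

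**With absorption, at steady state.** C(t) is proportional to exp(−ke·t)/(1 − exp(−ke·τ)) − exp(−ka·t)/(1 − exp(−ka·τ)). Here ke = ln 2/half-life, and ka is solved from Tmax = ln(ka/ke)/(ka − ke). At a half-life of 1 h, ka is 12.15 per hour for Tmax 0.25 h and 4.38 for 0.5 h. Accumulation is 1.004 and the trough is 0.5–0.7% of Cmax.

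Share of the interval below each fraction of Cmax (Tmax 0.5 h to 0.25 h):

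| Half-life | below 50% | below 25% | below 10% | below 5% |
|---|---|---|---|---|
| 0.75 h | 82–87% | 72–77% | 59–65% | 50–55% |
| 1.0 h | 80–84% | 66–71% | 49–54% | 37–42% |
| 1.5 h | 74–78% | 54–59% | 29–34% | 10–15% |

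**Chance of falling in the existing window.** The 30 (±15) minute window lasts 0.5 h, so the chance is 0.5/8 = 6.25%. A tracing taken inside it would be at about 75–100% of Cmax (half-life 1 h).

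**Per arm.** A Part 1 step of 30 subjects at 1:1:1 has about 10 per arm. Expected tracings in the window are 10 × 0.0625 = 0.6; at or above half of Cmax, 10 × 0.16 to 0.20, or about 2. With three arms in Part 2 (120/3 = 40 per arm), about 40 × 0.0625 = 2.5 would fall in the window. These counts assume that every subject is still on drug when the ECG is taken.

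**The case against.** The strongest reply is that ECG is a supporting measure here. The safety endpoints are SAEs and treatment-emergent AEs, and ECGs are summarised descriptively with no test or decision rule. The documents report no ECG signal. The Cmax-related effect they do describe, on blood pressure, is followed closely after every dose, with heart rate. This stands, and it limits how much rests on the point.

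The uniform-timing assumption is also open to challenge. Sites might cluster ECGs near dose-linked procedures or away from them, and the documents do not say which.

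Some stronger readings are tempting, but the documents do not support them:
- *That most tracings would be near trough or drug-free.* About four fifths fall below half of Cmax, but only about half fall below 10%, and fewer than half below 5% at a 1 h half-life.
- *That the ECG cannot show a drug effect.* About 16–20% of tracings would still be at or above half of Cmax, and an effect that lags or outlasts plasma levels could appear at any time.
- *That there is only ever one on-treatment ECG.* Extended dosing adds one on the last dosing day.
- *That 30 mg TID takes peak exposure beyond earlier experience.* The daily total is higher (90 mg against 60 mg at 30 mg BID). However, Protocol 1.2 reports single doses up to 80 mg, and 5.2 expects no significant accumulation on TID dosing.
- *That the DRC would be falsely reassured.* What it receives is set by its charter, which is not among these documents.

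**Conclusion.** The point holds as a limit on sensitivity. No section of either document ties the on-treatment ECG to a dose or uses time since dose in the analysis. Given the protocol's own pharmacokinetics and uniform ECG timing, about 80–84% of tracings would fall below half of Cmax and about half below 10% (29–65% across half-lives of 1.5 to 0.75 h). About 6% would fall in the 30 (±15) minute window. The ECG comparison with placebo therefore has low sensitivity to a Cmax-related effect.

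The missing timing is plain from the text. The percentages rest on the one-compartment model and on the timing assumption, and would shift if sites cluster their ECGs. The change is worth making because it is cheap, even though no ECG effect is reported in the documents.

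**What to change.** - **Protocol 3.1.1, 8.10, Appendix A and the synopsis:** schedule the existing Day 7 ECG, and the last-dosing-day ECG if dosing is extended, alongside the 30 (±15) minute post-dose vital signs.
- **Early discharge:** take the ECG in that window after the last dose given before discharge where feasible. Otherwise take it untimed, without delaying discharge.
- **eCRF:** record the ECG clock time. The exact dose time is already captured (Protocol 5.5.4), so time since dose can be derived.
- **SAP 3.6.4:** summarise in-window tracings separately from out-of-window and off-drug tracings, and add the last-dosing-day time point if dosing is extended.

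The cost is wording in both documents and one eCRF field. No extra ECG or visit is needed, because subjects already stay supine until the 90-minute vital signs. The drawbacks are less scheduling freedom on the ECG day, and some discharge tracings that will remain out of window.
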